7.3 Medical History

Medical history will be coded using Medical Dictionary for Regulatory Activities (MedDRA) version 24.1.

Medical/Surgical history will be summarized by treatment group with the number and percentage of subjects in each System Organ Class (SOC), Preferred Term (PT), and overall, for the Safety

CONFIDENTIAL Page 21 of 31

Private and Confidential Study No 21755 Date: DEC 18, 2023

Population. Subjects will be counted only once at the PT, only once at the SOC, and only once at subject level for the counting of total number of subjects with a medical history term.

Individual subject data listings for medical/surgical history will be presented.

7.4 Prior and Concomitant Medications

Prior medications are those medications that are taken prior to the first dose of study drug i.e., Prior medications have a stop date/time before study treatment starts. Medications stopped on the same day as the start of first study-drug administration will be considered as prior medication only. Concomitant medications are medications taken by subject on/after the start of first study-drug administration. If a medication starts before study entry and continues through the study that will be considered both as prior and concomitant. Prior and concomitant medications will be classified according to the World Health Organization Drug Dictionary (WHODD) version B3SEP2021.

Prior and concomitant medications will be summarized by Anatomical Therapeutic Chemical (ATC) classes and Preferred Term (PT) using number and percentages for Safety Population by treatment groups.

Individual subject data listings will be presented, with separate Listings for prior and concomitant medications.

7.5 Protocol Deviation

Protocol Deviation will be summarized by treatment groups and deviation categories (Major/Minor) using Safety Population.

Individual subject data listings for protocol deviations will be presented.

7.6 Study Drug Exposure and Overdose

For this study, any dose of study intervention greater than one (1) tablet being ingested will be considered an overdose. This includes tablets that were accidently swallowed requiring the subject to apply a second (backup) buccal tablet, applying two tablets to the gum, or any other situation in which a subject ingests two tablets.

Overdose for ITT and PP populations will summarize the number and percentage of subjects who self-administer a second tablet along with the reason for taking second tablet by treatment groups.

Individual subject data for overdose will be presented in Listing. Also, a listing will be presented all other overdoses where all other overdoses are defined as any reason other than these Accidentally

CONFIDENTIAL Page 22 of 31

Private and Confidential Study No 21755 Date: DEC 18, 2023

swallowed, Tablet did not stick to gum when applied and not swallowed Accidentally chewed will be considered as all other overdoses.

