6.1 Study Intervention Administered

During screening participants who meet the entry criteria will be sequentially assigned to a unique number in ascending order (randomization number, RNR) according to the

Page: 31 of 68

Version 5.0

randomization schedule prepared prior to the study. A separate kit number (and corresponding kit) will be assigned by the interactive (x-voice/web) response system (IXRS) that correlates to the blinded study intervention assigned when the subject was randomized.

Participants will be numbered according to the following scheme:

14001XXXXX

14 = country code (USA)

001 = site number (for site 1)

XXXXX = RNR (starting with 10001)

Whereas the "Xs" will be replaced with a five digit sequentially assigned number as each subject enters the study (e.g., first subject number at Site 1 of the study will be 1400110001).

Once a number has been assigned to a participant, it cannot be reassigned to another participant.

Participants who do not meet all of the eligibility criteria will not be randomized. Upon successful completion of all screening assessments, randomization and participant's receipt of study intervention, participants then enter the Run-In Phase in which they are eligible to start study intervention. At the first sign of prodromal symptoms, participants may self-initiate study intervention which automatically moves them into the Treatment Phase and one of two blinded study interventions:

- Sitavig® (acyclovir) 50 mg muco-adhesive buccal tablet (one tablet application on Day 1);
- Placebo muco-adhesive buccal tablet (one tablet application on Day 1).

Participants will apply one (1) muco-adhesive buccal tablet to the upper gum of the mouth on the same side of the mouth where the prodromal symptoms started. Any dosing-related deviations outside of the allowable window (e.g., >1 hour after the start of prodromal symptoms, second tablet administered) will be documented in the Science 37 Platform (see Section 6.5).

Study intervention is defined as any investigational intervention(s), marketed product(s) or placebo intended to be administered to a study participant according to the study protocol.

Version 5.0 Page: 32 of 68

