6.5 Study Intervention Compliance

Participants will be following the dosing instructions provided for applying a single buccal tablet to the upper gum on the same side of the mouth as the HL symptoms. Participants will record the date/time of dosing using the Science 37 Platform. Any deviations from the dosing instructions (e.g., greater than 1 hour after prodromal symptoms, applying a second tablet) will be recorded in the electronic case report form (eCRF) and/or Science 37 Platform.

For participants who self-administer a second tablet at the time of dosing (Day 1), the reason for applying a second tablet must be recorded in the eCRF and/or Science 37 Platform. Possible reasons are:

- Accidentally swallowed (see Section 6.8 related to an overdose);
- Tablet did not stick to gum when applied, not swallowed;
- Accidentally chewed, not swallowed;
- Lost/dropped first tablet, not used;
- First tablet was damaged, not used;
- Other (explanation not previously stated).

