9.2 Sample Size Determination

9.3 Analysis Set

For the purposes of analysis, the following analysis sets are defined:

Table 2 - Analysis Populations

| Participant Analysis Set | Description |
|--------------------------|--|
| Safety | All randomized subjects who take at least one dose of IMP. Safety analyses will be conducted on the safety population. |
| Intent To Treat (ITT) | All subjects who are randomized and provide at least one measure of primary efficacy parameters after the 1 st dose of IMP. |
| Per Protocol (PP) | The Per Protocol population will include all subjects in ITT who complete 14-days of evaluations and do not have any major protocol violations. Any exclusion from PP Population will be determined and documented prior to the database lock. |
| | The primary efficacy analysis population will be PP population and ITT Population will be secondary. The same analysis on ITT Population will be repeated for the primary and secondary efficacy endpoints to assess the robustness of the results based on PP Population. |

Version 5.0 Page: 49 of 68

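### SAP 7.6 counts every second-tablet user as an overdose, including those whose first tablet was never used, and its ITT and PP tables leave a separate coverage gap

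*SAP*

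**What the plan says.** SAP 7.6 (Study Drug Exposure and Overdose) opens with a definition that matches Protocol 6.8: "any dose of study intervention greater than one (1) tablet being ingested will be considered an overdose". It adds examples: "This includes tablets that were accidently swallowed requiring the subject to apply a second (backup) buccal tablet, applying two tablets to the gum". Further ways of ingesting two tablets are covered as well.

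The next paragraph sets the summary: "Overdose for ITT and PP populations will summarize the number and percentage of subjects who self-administer a second tablet", with the reason, by treatment group. Subject-level overdose data are to be listed. A further listing covers all other overdoses, where "all other overdoses are defined as any reason other than these", followed by three reasons: swallowed, did not stick, and chewed.

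Protocol 6.5 gives six possible reasons for a second tablet. One is "Lost/dropped first tablet, not used"; the damaged-tablet reason likewise says that the first tablet was not used. Only the swallowed reason is cross-referenced to the overdose section.

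On populations, SAP 6.1 defines Safety as all randomized subjects who took at least one dose. ITT also requires at least one post-dose face-image assessment. PP also requires 14 days of evaluations and no major protocol violation. Protocol 9.3 states: "Safety analyses will be conducted on the safety population".

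**The concern.** The definition turns on how many tablets were ingested, whereas the table turns on whether a second tablet was administered. These are different groups of people. Someone who dropped the first tablet and used the backup received one tablet, as intended, yet would be reported under overdose.

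This matters because SAP 7.6 is the only planned summary of overdose by that name. Protocol 10.3.1 says that overdose in itself is not reported as an adverse event unless it is intentional with possible self-harming intent, so the adverse event tables will not supply a corrected count. A study report that took its overdose figure from the 7.6 headline would give a number that does not match the definition printed above it.

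The choice of populations is a second and separate matter. Medical history, medications, protocol deviations, adverse events and vital signs are all summarised on the Safety population. Overdose is summarised on two smaller sets, and no reason is given.

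**Working it through.** The plan states no figure to reproduce, and the documents give no frequencies for the second-tablet reasons. The check sets each Protocol 6.5 reason against the definition (SAP 7.6, Protocol 6.8) and against the two SAP 7.6 outputs.

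| Reason for second tablet | Meets the definition? | In overdose summary? | In listing of all other overdoses? |
|---|---|---|---|
| First tablet swallowed | Yes | Yes | No |
| Did not stick, not swallowed | Unclear | Yes | No |
| Chewed, not swallowed | Unclear | Yes | No |
| Lost or dropped, not used | No | Yes | Yes |
| Damaged, not used | No | Yes | Yes |
| Other | Case by case | Yes | Yes |

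**Summary.** All 6 of 6 reasons are counted. Of these, 1 clearly meets the definition, 2 clearly do not, 2 depend on how ingestion and the two-tablets-on-the-gum example are read, and 1 depends on the individual case (1 + 2 + 2 + 1 = 6). Reasons counted without meeting the definition number at least 2, and at most 2 + 2 + 1 = 5.

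**Listing.** Removing the three named reasons leaves 6 − 3 = 3. Two of those three state that the first tablet was not used. The only reason that clearly meets the definition is outside this listing; it falls in the main overdose listing.

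**Populations.** By the SAP 6.1 definitions, PP lies within ITT, and ITT lies within the dosed subjects.

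- A dosed participant with no post-dose image assessment is in Safety but in neither ITT nor PP. If that participant ingested two tablets, neither overdose table shows it.
- Protocol 6.1 requires documentation of "Any dosing-related deviations outside of the allowable window (e.g., >1 hour after the start of prodromal symptoms, second tablet administered"), so second-tablet use is a recorded dosing deviation. If it were classed as major, PP would drop the people the table is meant to count. Neither document says that it is major.

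**Other outputs.** The deviation summary in SAP 7.5 uses the Safety population but is broken down only by Major and Minor category. The detachment, swallowing and replacement endpoints in SAP 7.7.3 are analysed on ITT. Neither gives an overdose count for all dosed participants.

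**The case against.** The strongest reply is that nothing is lost. The summary sentence runs "Overdose for ITT and PP populations will summarize the number and percentage of subjects who self-administer a second tablet along with the reason", and SAP 7.6 also requires subject listings, which it does not restrict to ITT or PP. Protocol 6.8 asks for the quantity of the excess dose, its timing and the reason to be documented. A reader can subtract the two rows in which the first tablet was not used. This stands. One might infer that the true number cannot be recovered from the report, but the documents do not support that for the rows with a clear status. It remains difficult only for the reasons whose status is undefined, and for dosed participants outside ITT, who could appear in listings but not in the table.

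A reader might also infer that using ITT and PP contradicts the overdose definition or breaks the rule on safety analyses. It does neither. The definition names no population. Protocol 9.4.5 and SAP 7.8 describe safety analysis as adverse events and vital signs, and overdose sits in the exposure section. What remains is a gap in coverage. It is probably small, since ITT needs only one usable post-dose image from a schedule of three a day through Day 14.

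It is likewise tempting to say that the PP table would show zero. That would follow only if every second-tablet use were classed as major, which no section states. The backup tablet is supplied for application problems, and the ITT table would still show the cases.

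Finally, the sentence defining the listing crosses a page break and is ungrammatical, so its intent is not certain. Read as written, it still takes in both reasons with an unused first tablet.

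**Conclusion.** The point holds as an internal inconsistency in SAP 7.6. Both the headline overdose count and the label on the second listing include participants who do not meet the SAP's own definition. At least two of the six Protocol 6.5 reasons are affected, and up to five depending on how the two not-swallowed reasons and the residual category are classified. This rests on the wording alone. Because the documents give no frequencies, no inflation factor can be stated, and the count of reasons must not be read as a proportion of participants.

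The ITT and PP tables are a distinct coverage gap, confined to dosed participants without a post-dose image and, for PP, to those removed for incomplete evaluations or major violations.

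Severity is minor. The table is descriptive and carries no test, and neither the efficacy results nor the adverse event summaries depend on it.

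**What to change.** In SAP 7.6 and the matching table shells:

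1. Count as overdose only participants who meet the definition given in that section, and tabulate them on the Safety population.
2. Report second-tablet use by reason in a separate exposure or compliance table, not under the overdose heading.
3. Take the two reasons with an unused first tablet out of the listing of all other overdoses, and rewrite the sentence that defines it.
4. Have the sponsor reconcile SAP 7.6 with Protocol 6.5 and 6.8 on how the two not-swallowed reasons (did not stick, chewed) and the residual category are classified, and record the rule before database lock. That classification is the sponsor's decision.

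The cost is SAP and shell wording. The reasons are already collected in the eCRF or platform, so no new data are needed, and moving to the Safety population only adds dosed participants who are already in the database.

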7.7 Efficacy Analysis

7.7.1 Analysis of Primary Efficacy Endpoint

The primary efficacy variable is DOE, which will be measured in hours (using the Science 37 Platform), of a single treated HL lesion. Observation period to determine healing will last up to 14 days. DOE is defined in detail in section 4.

DOE will be analyzed using Kaplan-Meier method for treatment groups (Sitavig and Placebo). Median, associated 95% CIs and survival probabilities will be estimated using Kaplan-Meier (KM) Method. DOE curves between the two treatment groups will be compared with a log-rank test and the corresponding hazard ratio (with 95% CI) will be estimated using Cox proportional hazard method.

The analysis of primary efficacy endpoint will be performed on both ITT and PP population, with PP population being the primary efficacy population and ITT population being secondary. Individual subject data for DOE will be presented in Listing.

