8.1.4 Treatment/Evaluation Phase (Day 1)

Participants who start to experience prodromal symptoms before the visible appearance of any signs of HL must document the start time of symptoms in Science 37 Platform, complete a pre-dose (immediately before dosing) 0-10 NRS cold sore symptom evaluation (pain, burning sensation, itching and swelling) and a face image. Prior to the start of study intervention, all WOCBP participants MUST perform a urine pregnancy test, and verify that the results are negative (not pregnant), and record in the Science 37 Platform. After verification of a negative pregnancy test result, the participant may self-initiate study intervention.

Any participant who has a positive pregnancy test or is not sure of the results must contact the Science 37 study team immediately. Participants with a verified positive pregnancy test must not self-administer study intervention and will be withdrawn from the study.

Participants must always record pre-dose NRS and a face image irrespective of the start time of prodromal symptoms in the Science 37 Platform. After the completion of all pre-dose procedures, participants will be instructed to self-administer one (1) tablet. Should the buccal tablet adhere to the upper gum correctly, a second dose/tablet is NOT applied. A second tablet in the treatment kit is provided and labeled "BACKUP". The backup tablet should only be used if an issue occurs applying the first tablet (see Section 6.5).

After dosing, participants will complete the 0-10 NRS cold sore symptom evaluation, and face images at 09:00, 14:00 and 19:00 that day within Science 37 Platform. Depending on time of day study intervention is started, some Day 1 assessments and face images may not be collected if the time (minus the 60 minute window) occurs before the time of dosing. If dosing is started after 19:00, then post-dose NRS and face images will be collected starting the next day at 09:00. All post-dose time point assessments (NRS and face images) have an allowable window of ± 60 minutes.

Version 5.0

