9.4.2 Primary Endpoint

The primary efficacy variable is:

• Duration of episode (DOE) will be measured in hours (using the Science 37 Platform), of a single treated HL lesion. Observation period to determine healing will last up to 14 days (DurEp14).

Duration of episode (DOE) is defined as the time from the initiation of treatment (study intervention) to the healing of primary lesions (loss of crust) for participants who experience a vesicular lesion. For participants whose primary lesions are not vesicular in nature, duration of episode is the time from study intervention initiation to the return to normal skin as determined by the independent blinded reader of the participant's face images using a 6-point Likert scale or the cessation of symptoms, whichever comes last. For the subjects who do not demonstrate the healing of primary lesions or cessation of symptoms, the data will be censored at 14 days (14*24 hours) or time of loss of follow-up, whichever happens earlier.

Duration of episode (DOE) will be estimated and plotted using Kaplan-Meier method and analyzed using log-rank test.

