2.3 Determination of Sample Size

CCI

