2.4 Randomization

Subjects will be randomized in a 1:1 ratio to either of the treatment groups (Sitavig or placebo). At Screening, qualified subjects will be assigned a unique number (Randomization Number, [RNR]) in ascending numerical order according to the randomization schedule generated prior to the study by Statistics Department at Bayer.

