3 DATA ANALYSIS CONSIDERATION

3.1 General Data Considerations

The following conventions will be applied to analyses/data presentation:

All dates will be displayed in DDMMMYYYY format.

The statistical analyses will be performed by Quartesian (now a part of Veranex Solutions), using Statistical Analysis System (SAS) Version 9.3 (or higher). All Tables, Figures, and Listings (TFLs) will be produced in landscape format. In general, all data will be listed by the subject, treatment and visit but not limited to above variables. The number of variables presented in each Listing can vary. Please refer to Mock TFLs.

Data will be summarized by treatment wherever appropriate. The total number of subjects in the study group (N) under the stated population will be displayed in the header of summary tables. Unscheduled visit data will be presented in Listings, but not in Tables and Figures.

Data will be summarized using descriptive statistics for continuous variables. Unless otherwise stated, descriptive statistics will include total number of subjects with non-missing value of a variable/parameter (n), mean, Standard Deviation (SD), minimum, median, and maximum. The number of missing observations will also be presented, if there are any, at a particular visit. In case

CONFIDENTIAL Page 14 of 31

Private and Confidential Study No 21755 Date: DEC 18, 2023

of n<2, where n indicates the number of evaluable subjects at a particular time point, only n, minimum and maximum will be displayed.

For categorical variables, data will be summarized using number and percentages. The number (n) indicates the number of subjects with a particular value of a variable or event, which should always be less than or equal to the total number of subjects in the respective treatment group (N). The number and percentage of subjects with missing values for a variable/category/event will also be presented, if there are any, for the resulting visits under the "Missing" category.

Unless otherwise stated, all percentages will be expressed to one decimal place. The number and percentage of subjects will always be presented in the form XX (XX.X). Counts of zero in any category will be presented as "0" and if the percentage in any category to be presented is 100, it will be presented as "100".

All statistical testing will be 2-sided at significance level of 0.05 and no multiplicity adjustment will be made.

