4 DEFINITIONS AND DERIVATIONS

Run-in Failures: Run-in failures are participants who successfully completed screening and randomized to a blinded study intervention (treatment). Participants start a 6-month eligibility window during the Run-in Phase where they could potentially self-initiate treatment. Participants who are considered a Run-in failure occur because of the following:

- Randomized participants with no prodromal symptoms after 6 months
- Met an exclusion criterion (e.g., medication, pregnancy)
- Adverse event or change in medical history that requires study withdrawal
- Withdraw of informed consent by the participant
- Study intervention kit not available
- Lack of compliance as determined by the Investigator/designee

Baseline: Baseline value is defined as the last non missing assessment prior to first administration of the study drug. If the assessment occurs on the same day as the first study drug administration, then the time of assessment should be compared to the time of first dose administration to derive the baseline value.

Post-baseline: The Post-baseline values are defined as assessments taken after the first administration of study drug/treatment.

Change from Baseline = $(post\ baseline\ value - baseline\ value)$.

Duration of Episode (DOE): DOE is defined as the time from the initiation of treatment to the healing of primary lesions (loss of crust) for subjects who experience a vesicular lesion. For subjects whose primary lesions are not vesicular in nature, DOE is the time from study intervention initiation to the return to normal skin as determined by the independent blinded reader of the subject's face images using a 6-point Likert scale or the cessation of symptoms, whichever comes last. For the subjects who do not demonstrate the healing of primary lesions or cessation of symptoms, the data will be censored at 14 days (14*24 hours) regardless of any circumstances. If time (hour) is missing for either treatment initiation or the healing of primary lesion or both, however, both dates are recorded, then DOE is number of days (end date – start date) *24. If only healing ending date and/or time are missing, DOE will be imputed as 14*24 hours. If date of treatment initiation is missing, then DOE will be missing.

CONFIDENTIAL Page 17 of 31

Private and Confidential Study No 21755 Date: DEC 18, 2023

DOE (hours) = (Date and time of healing of primary lesions – Date and time of first treatment administered)

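### The primary comparison of episode duration uses none of the pre-dose stage and timing data already recorded; if those data predict healing, adjusting for them would gain power at little cost

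*SAP*

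**What the plan says.** Protocol 9.4.2 gives the primary analysis as: "Duration of episode (DOE) will be estimated and plotted using Kaplan-Meier method and analyzed using log-rank test". SAP 7.7.1 repeats the two-group comparison ("DOE curves between the two treatment groups will be compared with a log-rank test") and adds that the "hazard ratio (with 95% CI) will be estimated using Cox proportional hazard method". Neither section lists a covariate or a stratum. SAP 2.4 describes 1:1 randomization without naming a stratification factor. The per-protocol (PP) population is primary and ITT is secondary.

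On data capture, Protocol 8.1.4 states: "Participants must always record pre-dose NRS and a face image irrespective of the start time of prodromal symptoms". It also requires the symptom start time to be documented. Protocol 6.5 has the dosing date and time recorded. Protocol 8.2.4 has pre-dose as well as post-dose images read by a blinded reader on a scale from 0 (normal lip) to 5 (crust).

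Time from prodrome is used once in the efficacy analyses: SAP 7.7.3 splits DOE at 1 hour, as an other endpoint on ITT. For aborted lesions, SAP 7.7.2 plans a chi-square or Fisher test with no adjustment.

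**The concern.** DOE runs from dosing to healing, and participants choose when to dose. Someone who doses further into an episode, or with a more advanced lesion, may have a different amount of time left from someone who doses at the first tingle. Stage also decides which healing rule applies. Under SAP section 4, a vesicular lesion heals when its score falls to 0 or 1. A non-vesicular lesion needs a score of 0 and all symptom scores at 0.

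In a proportional-hazards setting, leaving out a prognostic variable has two effects even under perfect randomization: the estimated hazard ratio moves toward 1, and the test loses power. The variables at issue arise after randomization but before treatment and under blinding, so adjusting for them is legitimate. At stake is power in the primary comparison that could be had from data the trial already collects.

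**Working it through.** **No plan figure to reproduce.** The content of SAP section "2.3 Determination of Sample Size" is redacted and no text is visible under Protocol 9.2. Sample size, events, design effect and planned power are therefore unknown. No passage links the pre-dose variables to DOE. What follows is illustration.

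**Inputs from the documents.** Two-sided 0.05, no multiplicity adjustment (SAP 3.1). Allocation 1:1 (SAP 2.4). For those who do not heal, "the data will be censored at 14 days (14*24 hours) regardless of any circumstances", that is 336 h. Cold sores last around 7 to 10 days (Protocol section 2).

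**Assumed inputs.** Weibull proportional hazards with shape 2. Placebo median 8 days (7 also tried). One normal score *x* stands for the three covariates combined: hazard = h0(t)·exp(β·arm + x), with x of standard deviation SD.

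**Meaning of SD.** The share of log healing-time variance explained is R² = SD²/(SD² + π²/6), with π²/6 = 1.645:
- SD 0.1: 0.01/1.655 = 0.6%
- SD 0.2: 0.04/1.685 = 2.4%
- SD 0.3: 0.09/1.735 = 5.2%
- SD 0.5: 0.25/1.895 = 13%
- SD 0.7: 0.49/2.135 = 23%

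**Simulation A.** 250 per arm, conditional hazard ratio 1.29, 3,000 trials per setting. Monte Carlo error per power is √(0.75×0.25/3000) ≈ 0.8 point.

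| SD | Unadjusted power | Adjusted power | Gap (points) | Unadjusted HR |
|---|---|---|---|---|
| 0 | 78% | 77% | none beyond noise | – |
| 0.1 | – | – | under 1 | – |
| 0.2 | – | – | about 2 | – |
| 0.3 | 73% | 78% | 5 | 1.28 |
| 0.5 | 63% | 76% | 13 | 1.25 |
| 0.7 | 54% | 76% | 22 | 1.22 |

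The rows for 0.1 and 0.2 come from a second run with placebo medians of 7 and 8 days. That run gave about 5, 12 to 13 and 21 points at SD 0.3, 0.5 and 0.7.

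**Simulation B.** Sized by Schoenfeld's formula for HR 1.30 and 80% power: events = 4(1.960 + 0.842)²/(ln 1.30)² = 31.4/0.0688, rounded up to 457. N = 457/0.90 ≈ 508. There were 2,000 trials per setting (error about 1 point), comparing the log-rank test with the adjusted Cox Wald test. The N ratio is the sample size needed with adjustment relative to the log-rank test, ((1.96 + z_adjusted power)/(1.96 + z_log-rank power))⁻².

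| R² | Log-rank | Adjusted Cox | Gap (points) | Unadjusted HR | N ratio |
|---|---|---|---|---|---|
| 0 | 81% | 81% | 0 | 1.30 | 1.00 |
| 0.02 | 77% | 80% | 2 | 1.29 | 0.94 |
| 0.05 | 75% | 79% | 4 | 1.28 | 0.90 |
| 0.10 | 70% | 79% | 9 | 1.27 | 0.80 |
| 0.20 | 60% | 79% | 19 | 1.24 | 0.64 |
| 0.30 | 50% | 77% | 27 | 1.21 | 0.53 |

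Gaps are taken before rounding. Worked N ratio at R² 0.10: log-rank power 69.7% gives z = 0.52 and adjusted power 78.8% gives z = 0.80, so (2.48/2.76)² ≈ 0.80.

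Under no treatment effect with R² 0.20, rejection rates were 4.3% (log-rank) and 3.8% (adjusted), so neither test exceeded its nominal size. The two simulations agree at matching R².

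**Caveat on the assumed hazard ratio.** The earlier trial's reduction was 0.57 days (Protocol 2.2), on a different endpoint. Over a 7 to 10 day placebo median with shape 2 it would imply (1 − 0.57/7)⁻² = 1.19 down to (1 − 0.57/10)⁻² = 1.12. The value of about 1.3 is therefore an assumption, not a figure from the documents.

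**Aborted lesions.** No simulation is needed. SAP section 4 requires that an aborted lesion never reach a score of 3 or above before healing. A lesion already at 3 or more at dosing is a non-event in either arm, whatever the treatment does.

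**The case against.** The strongest reply is that the prognostic premise is unproven. The nearest statement, at the end of Protocol 2.2, concerns a larger treatment difference with application within 1 hour, which is not prognosis for DOE. Even the direction is unclear: a pre-dose score of 0 may precede a short aborted episode or a full vesicular course.

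The design may also leave little spread to adjust for. Dosing is preferred within an hour and before visible signs (Protocol 4.1.1.3), so image scores may cluster at 0. Dosing after 1 hour is recorded as a deviation (Protocol 6.1 and 6.5). If that counts as major, which the documents do not say, the primary PP set narrows time from prodrome further. All of this stands, and it is why the loss is stated as conditional.

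A reader might infer that the trial is underpowered. The documents do not support that, because the sizing basis is redacted. If the trial was sized at 80% on the marginal log-rank effect, that power is intact and adjustment only adds to it: about 84%, 88% and 94% at R² 0.05, 0.10 and 0.20.

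A reader might also infer that chance imbalance in stage invalidates the log-rank test. It does not. The test matches the randomization described, and its error rate already allows for chance imbalance. Nor do the documents show that anyone will have a vesicle at dosing; they only leave it possible.

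**Conclusion.** The point holds as an inexpensive efficiency improvement. The primary analysis is unadjusted, and the three variables are required before dosing and can properly be adjusted for. If they are prognostic, the planned analysis understates the conditional hazard ratio and forgoes power.

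The size depends on a strength of association that the documents do not supply. Under the stated assumptions it ranges from nothing to about 5 points for weak covariates, and reaches 12 to 13 or 21 to 22 points for moderate or strong ones. Confidence is high in the omission and the mechanism, and low in any single figure. It would be wrong to say that the plan ignores time from prodrome altogether, since SAP 7.7.3 uses it for an other endpoint; the omission concerns the primary analysis.

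**What to change.** Before unblinding:

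1. **Reconcile the pre-dose symptom items.** Protocol 8.1.4 lists pain, burning sensation, itching and swelling. Protocol 8.2.1 lists pain, tenderness, itching, tingling and discomfort. A pre-dose total is undefined until these agree.
2. **Amend SAP 7.7.1.** Make the primary comparison a Cox model with treatment, pre-dose image score (as categories, with sparse ones collapsed by a stated rule), pre-dose NRS total, and time from prodrome to dosing with its functional form stated. A log-rank test stratified by pre-dose image score is a simpler alternative. Keep the unadjusted log-rank test and Kaplan-Meier estimates as supportive.
3. **State a missing-covariate rule.** The SAP section 4 baseline is the last non-missing value before dosing. If the Day 1 pre-dose record is missing, that rule could bring in a screening value taken without symptoms, which says nothing about stage at dosing.
4. **Adjust or stratify the aborted-lesion comparison** in SAP 7.7.2 by pre-dose image score.
5. **Record the departure** from Protocol 9.4.2 in SAP 7.13.

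If the sponsor prefers not to change the protocol's primary test, a prespecified adjusted supportive analysis is the minimum, though it would not raise the power of the primary test.

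The cost is analysis wording and a 7.13 entry, with no new data collection. The downside is that the hazard ratio becomes conditional on the covariates and must be reported as such.
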